### 9.1.3 Clinical Trial Drug Assignment

On Day 1, subjects will be assigned a randomization number in ascending numerical order at each trial site. The randomization number encodes the subject assignment to either the TAK-418 or the placebo arm of the trial, according to the randomization schedule generated before the trial by the sponsor's Statistics Department. Each participant will be dispensed blinded trial treatment, labeled with his/her unique randomization number, throughout the trial.

#### 9.1.4 Inclusion and Exclusion Criteria

Each subject is assessed through randomization, according to the eligibility criteria provided in Section 7.0.

### 9.1.5 Medical History, Medication History, and Demographics

Qualified site personnel are to collect subject significant medical history (past and concurrent) per the site's standard of care and appropriate clinical judgment and subject demographics.

Qualified site personnel are to review subject prior and concomitant medication use. Medications are defined as prescription and over-the-counter drugs, vitamin supplements, nutraceuticals, and oral herbal preparations.

#### 9.2 Clinical Procedures and Assessments

### 9.2.1 Full Physical Examination

Qualified site personnel will conduct full physical examinations.

## 9.2.2 Neurological Examination

Qualified site personnel will conduct full neurological examinations.

# 9.2.3 Height and Weight

Body weight and height will be obtained with the subject's shoes off, and jacket or coat removed.

### 9.2.4 BMI

BMI equals a person's weight in kilograms divided by height in meters squared (BMI=kg/m^2). Body weight and height will be obtained with the subject's shoes off and jacket or coat removed.

BMI will be rounded to the nearest whole number according to the standard convention of 0.1 to 0.4 round down and 0.5 to 0.9 round up.

### 9.2.5 Vital Signs

Body temperature will be measured with an oral (temperature taken at floor of the mouth) or tympanic thermometer. The same method (eg, oral or tympanic) must be used for all subsequent measurements for each individual subject and should be the same for all subjects.

Subjects should rest in a semirecumbent position for at least 5 minutes before having vital sign measurements obtained. Vital signs will include HR, SBP, and DBP. The same method (eg, same size cuff, manual or automated) must be used for all measurements for each individual subject and should be the same for all subjects.

Subjects will continue to rest in a semirecumbent position from the time of dosing until 4 hours postdose except to stand for the measurement of standing vital signs (if needed) or other trial-related procedure.

#### 9.2.6 12-Lead ECG

Special care must be taken for proper lead placement by qualified personnel. Skin should be clean and dry before lead placement. Subjects may need to be shaved to ensure proper lead placement. Female subjects may need to remove their bra.

Subjects should be resting in a semirecumbent position for at least 5 minutes before each ECG measurement

QT intervals with QTcF will be used to calculate QT intervals in this trial.

Before each treatment period/cohort, a predose ECG will be obtained within approximately 1 hour before dosing of TAK-418. This measurement will be used as the baseline. The principal investigator should arrange to have a trial cardiologist available as needed to review ECG tracings with abnormalities.

During each treatment period, if a subject demonstrates an increase in QTcF interval ≥40 msec compared with a predose baseline measurement, the ECG will be repeated within 5 minutes. The average value of the QTcF interval from the 2 ECGs will represent the value at that time point. If the average QTcF interval increase from Baseline for any postdose time point is ≥40 msec, the subject will continue to be monitored by repeat 12-lead ECGs every 60 minutes for at least 4 hours or until the QTcF is within 40 msec of the baseline value. If prolongation of the QTcF interval ≥40 msec persists, a consultation with a trial cardiologist may be appropriate and the sponsor should be notified.

If the QTcF interval is  $\geq$ 500 msec, the sponsor should be notified and the ECGs should be reviewed by a cardiologist. The subject should be telemetry-monitored (until the QTcF is <500 msec) or should be considered for transfer to a location where closer monitoring is available.

If the subject has unstable hemodynamics, or has any clinically significant dysrhythmias noted on telemetry, the subject should be immediately transferred to an acute care setting for definitive therapy.

If repeat ECGs are required, the clinical site will decide whether to leave the electrodes in place or mark the position of the electrodes for subsequent ECGs. To mark the position of the electrodes, 12-lead electrode sites will be marked on the skin of each subject with an ECG skin marker pen to ensure reproducible electrode placement.

[figure not shown]
The following ECG parameters will be recorded: HR, PR-interval, QRS-duration, QT-interval, QTcF-interval, and the interpretation of the ECG profile by the principal investigator.

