### 11.0 STATISTICAL METHODS

### 11.1 Statistical and Analytical Plans

A statistical analysis plan (SAP) will be prepared and finalized before unblinding of subject's treatment assignment. This document will provide further details regarding the definition of analysis variables and analysis methodology to address all trial objectives.

A targeted data review will be conducted before unblinding of subject's treatment assignment.

This review will assess the accuracy and completeness of the trial database, subject evaluability, or appropriateness of the planned statistical methods.

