7.11.3 Vital Signs

Descriptive statistics (N, mean, SD, median, minimum, and maximum) will be used to summarize vital sign parameters at baseline, each post-baseline visit, and change from baseline

to each post-baseline visit. Summaries will be presented by pooled placebo and each TAK-418 dose level

Individual results of vital signs that meet Takeda's markedly abnormal criteria (see Appendix B) will be summarized and provided in the data listings. If a subject has a MAV for a particular vital sign parameter, all visits for that subject for that parameter will be listed. The number and percentage of subjects with at least 1 postdose MAV signs measurement will be summarized by pooled placebo, each TAK-418 dose level and TAK-418 overall. The mapping of the subjects who meet the MAV criteria will be listed as a table. All observations, including ones at unscheduled visits, will be included in the MAV evaluation and summaries.

All vital sign results for all subjects in the Safety Set will be listed by subject in the data listings and markedly abnormal values will be flagged.

7.11.4 12-Lead ECGs

The scheduled 12-lead ECG data will be collected according to Appendix D. The ECG parameters include heart rate, PR-interval, QRS-duration, QT-interval, and QTcF interval, and the interpretation of the ECG profile by the principal investigator.

Descriptive statistics (N, mean, SD, median, minimum, and maximum) of ECG parameters will be presented for baseline, each post-baseline visit, and changes from Baseline in quantitative ECG parameters to each post-baseline visit. Only the scheduled measurements will be included in the summary. No inferential statistics will be presented.

Individual results of quantitative ECG parameters from the 12-lead safety ECGs that meet Takeda's markedly abnormal criteria (see Appendix C) will be summarized and provided in the data listings. Shift tables will be generated to show the investigator's ECG interpretations at each postdose collection by the interpretation at Baseline.

All ECG data will be presented in the listings. ECG MAVs will be flagged in the listings.

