7.13 Changes in the Statistical Analysis Plan

Not applicable.

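### Do the protocol and the SAP disagree on which QTcF value counts when an ECG is repeated?

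*Protocol*

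**What the plan says.** **Protocol 9.2.6.** If QTcF is up by 40 msec or more "compared with a predose baseline measurement, the ECG will be repeated within 5 minutes". Then "The average value of the QTcF interval from the 2 ECGs will represent the value at that time point". If the averaged rise is still 40 msec or more, hourly ECGs follow. The averaging rule names QTcF only, although each tracing yields more: "The following ECG parameters will be recorded: HR, PR-interval, QRS-duration, QT-interval, QTcF-interval".

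**SAP 7.11.4, descriptive summary.** "The scheduled 12-lead ECG data will be collected according to Appendix D". Appendix D shows one ECG per time point (postdose: 1, 2 and 24 hours and Day 14) and no repeat. Directly after the sentence on descriptive statistics comes: "Only the scheduled measurements will be included in the summary".

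**SAP 7.11.4, MAVs.** A separate paragraph says that "Individual results of quantitative ECG parameters from the 12-lead safety ECGs" meeting Appendix C are summarized and listed. Protocol 11.1.6.4 describes the MAV review in nearly the same words. All ECGs are listed and MAVs are flagged.

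**Related text.** SAP 7.11.2 (laboratory) and 7.11.3 (vital signs) say outright that unscheduled readings count toward MAVs. SAP 5.1 makes an ECG MAV at least once postdose a component of the primary endpoint. For QTcF, Appendix C flags 500 msec or more, or a change of 30 or more together with a value of 450 or more. It has separate rows for QT and heart rate. Protocol 11.1 says of the SAP: "This document will provide further details regarding the definition of analysis variables and analysis methodology to address all trial objectives". SAP 7.13, "Changes in the Statistical Analysis Plan", records none.

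**The concern.** Read in isolation, SAP 7.11.4 seems to replace the protocol's value with another. Appendix D has no repeat ECG, so a programmer working only from the SAP might enter the first reading, while one working from the protocol would enter the average. Three further points add to the doubt:

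- ECG is the one safety domain where the protocol itself generates extra readings, yet it is the only MAV section with no sentence on unscheduled ones.
- Neither document has a repeat-reading rule for QT or heart rate, which have their own MAV limits.
- The protocol hands the definition of analysis variables to the SAP, so silence there looks like an omission.

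The stake is a count in the primary endpoint. With 6 active subjects per dose, one subject classified differently is 1/6 = 16.7 percentage points; in the pooled placebo group of 10 it is 1/10 = 10 points.

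**Working it through.** The plan gives no figure to reproduce. The check has three steps: whether the texts conflict, what each reading rule does to a subject, and how often the rule could matter.

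**1. The texts side by side**

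| Use | Protocol | SAP 7.11.4 | Combined reading |
|---|---|---|---|
| QTcF by time point | 9.2.6: the average is the value at that time point | Scheduled measurements only | The average is the value at the scheduled 1, 2 or 24 hour or Day 14 point; hourly repeats stay out |
| QT and heart rate by time point | No averaging rule | Scheduled measurements only | The scheduled tracing supplies them |
| MAV count | 11.1.6.4: individual results | Individual results | Each reading is tested against Appendix C |

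The scheduled-only sentence belongs to the descriptive summary; the MAV paragraph has no such limit. Protocol 9.2.6 never mentions the markedly abnormal criteria, so nothing in it requires the average to replace single readings in that count.

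**2. Effect on one subject**

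All readings are assumed, in msec, and each first reading meets the 40 msec trigger.

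| Baseline / first / repeat | Average (change) | First | Repeat | Average | Any reading |
|---|---|---|---|---|---|
| 420 / 462 / 430 | 446 (+26) | MAV | no | no | MAV |
| 412 / 454 / 440 | 447 (+35) | MAV | no | no | MAV |
| 405 / 447 / 455 | 451 (+46) | no | MAV | MAV | MAV |
| 440 / 502 / 490 | 496 (+56) | MAV | MAV | MAV | MAV |

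So the rule can matter in principle. The first row also moves the mean change of a 6-subject group by (42 − 26)/6 = 2.7 msec.

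The last column holds in general. The larger of two readings is never below their average, so if the average passes an upper limit and its change criterion, so does the larger reading. The same holds for lower limits with the smaller reading. Testing individual readings therefore never misses a subject whom the average would flag.

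For QT, Fridericia gives QT = QTcF × (60/HR)^(1/3). At heart rate 50 the factor is 1.063, so QTcF 433 gives QT 460 (a MAV), and a repeat of 420 gives 446. At heart rate 60 the factor is 1, and QT equals QTcF. The example needs a heart rate at the lower limit of the resting range allowed by exclusion criterion 20.

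**3. How often a repeat is triggered**

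The documents give no QTcF variance. Assume independent single-reading errors with SD 8 and a true rise of 10 at 1 and 2 hours, none at 24 hours or Day 14.

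- SD of a difference from baseline: 8 × √2 = 11.3.
- At 1 or 2 hours: z = (40 − 10)/11.3 = 2.65, probability 0.0040 each.
- At 24 hours or Day 14: z = 40/11.3 = 3.54, probability 0.0002 each.
- Upper bound for any trigger: 2 × 0.0040 + 2 × 0.0002 = 0.0084.

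Simulation over rises of 0 to 10 and SD 6 to 8 gave at most 0.8% of subjects, or 0.008 × 30 = 0.24 of the active subjects. Without a trigger there is no 5-minute or hourly repeat, so this also bounds the effect for QT and heart rate, apart from ECGs done unscheduled for other reasons.

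In the same model (true baseline normal, mean 400 to 420, SD 15, capped at 450), first reading minus average in the share of subjects with a QTcF MAV was:

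| True rise (msec) | SD 6–8 | SD 12 |
|---|---|---|
| 0–10 | 0 to 0.2 points | 0.2 to 1.9 points |
| 20 | 0.1 to 1.2 points | 2.2 to 3.9 points |
| 30–60 | up to 4.6 points | up to 6.7 points |

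The mean QTcF change differed by at most 0.04 msec at rises of 0 to 10 and SD 6 to 8.

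**The case for a change.** The strongest case for a change is that no SAP sentence says the average is the scheduled value. A reader could also hold that individual results means one result per time point. The listings would let someone find a discrepancy, but they do not fix the reported count. Settling the rule before unblinding costs two or three sentences and removes a later choice about a primary-endpoint component.

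The factual part stands: SAP 7.11.4 does not restate the averaging rule and lacks the sentence on unscheduled readings found in its two neighbours. The inference that the texts conflict does not. An SAP written to a protocol does not cancel a value definition by leaving it unrepeated, and an empty section 7.13 fits an intention to follow the protocol at least as well as an oversight.

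Making the average the tested value for Appendix C would be a choice in its own right. In the model at baseline 410, SD 8 and a true rise of 40, the average flags 53.2% of subjects, first or repeat 60.4%, and 50.0% are true MAVs. The average misclassifies 15.1%, against 20.8% for first or repeat. That advantage depends largely on the assumed independence of errors. Against it, the average can drop a qualifying reading from a safety count defined as at least once postdose: in that setting the first reading flags 5.5% of subjects whom the average does not. Counting single readings also matches the laboratory and vital-sign sections. This is a fair trade-off, and the plan's wording already leans to the more inclusive side.

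**Conclusion.** No change is needed. An analyst with both documents would put the two-ECG average into the QTcF summary at the scheduled time point, take QT and heart rate from the scheduled tracing, and test individual readings for MAVs. The SAP's silence is missing detail, not a contradiction.

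The expected effect is negligible: at most about 0.24 of 30 active subjects would have a triggered repeat at true rises of 0 to 10 msec and a reading SD of 6 to 8. Those inputs are assumptions. If QTcF rose by around 40 msec, the rules would differ visibly (53.2% against 60.4% in the setting above, or 3.2 against 3.6 subjects of 6), but more than half of the dose group would be flagged either way and the safety message would be the same. Protocol 6.3.2 gives no basis for expecting such rises: it reports an effect on hERG current in vitro but none on ECG parameters in telemetrized monkeys through 100 mg/kg. No test or formal decision threshold depends on the count, and every individual ECG remains visible in the listings.

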### 9.2.7 Trial Drug Administration

For the trial, trial drug (or placebo) will be administered in the manner described in Section 7.4.1.

### 9.2.8 BL-VAS

The Bond-Lader Visual Analogue Scale (BL-VAS) of Mood and Alertness consists of a questionnaire of 16 analogue scales that derive 3 factors that assess change in Self-Rated Alertness, Self-Rated Calmness, and Self-Rated Contentment. It has proven sensitivity to a wide range of compounds. In the original versions, ratings were performed by the subject by marking a point on a 10 cm line that is meant to represent the full range of the particular dimension (for example, alert—drowsy). Nine items assess alertness, 5 items assess contentedness, and 2 items assess calmness. A mark on the far left side or far right side of the scale represents extremes with regard to the adjectives on each side of the line (eg, a higher or more rightward score on a scale marked awake—drowsy indicates that the subject feels drowsier).

## 9.2.10 AE Monitoring

AE monitoring begins following signing of informed consent. Changes in subject health status from baseline assessment to trial drug administration should be captured in the subject's medical history. A complete description of AE collections and procedures is provided in Section 10.0.

# 9.2.11 Laboratory Procedures and Assessments

Laboratory samples will be collected in accordance with acceptable laboratory procedures. Samples will be taken following a minimum 8-hour overnight fast on the days stipulated in the Schedule of Trial Procedures (Section 3.0).

# 9.2.11.1 Clinical Laboratory Tests

# **Hematology**

Hematology will consist of the following tests:

Erythrocytes (RBCs)	Hemoglobin
Hematocrit	Platelets
Leukocytes (white blood cells [WBCs]) with absolute differential	

## Urinalysis

Urinalysis will consist of the following tests:

Protein	Glucose
Blood	Nitrite

Urine microscopy will be performed if urinalysis is abnormal. Microscopy consists of RBC/high-power field, WBC/high-power field, and casts.

# **Chemistry**

Chemistry evaluations will consist of the following standard chemistry panel:

Albumin	Alkaline phosphatase
ALT	AST
Blood urea nitrogen	Calcium
Carbon dioxide	Chloride
Creatinine	Glucose
Gamma-glutamyl transferase	Sodium
Potassium	Bilirubin (total), if above ULN total bilirubin will be fractionated
Protein (total)	

# 9.2.11.2 Diagnostic Screening

### Serum

Serum diagnostic evaluations will include the following tests:

HIV	Hepatitis Screen (HBsAg, hepatitis C virus antibody)
β-human chorionic gonadotropin (females only)	CCI
CCI	
CCI	

### Alcohol Screen

Subjects will undergo an alcohol breath test. A urine alcohol test may be performed at the discretion of the investigator.

#### Urine

A urine drug screen will include the following tests:

Amphetamines	Cotinine
Barbiturates	3,4-methylenedioxy-methamphetamine (MDMA)
Benzodiazepines	Methadone/metabolite
Buprenorphine/metabolite	Opiates
Cannabinoids	Oxycodone/oxymorphone
Cocaine/metabolites	Phencyclidine

CCI

[figure not shown]
### 9.2.12 C-SSRS

Suicidal ideation will be assessed using the C-SSRS at the times stipulated in the Schedule of Study Procedures (Section 3.0).

Two versions of the C-SSRS will be used in this trial: the Screening/Baseline C-SSRS Lifetime and the Since-Last-Visit C-SSRS.

# 9.3 Biomarker, PK, PD, and PGx, Samples

[figure not shown]
Samples for PK, PD, and or other biomarker analysis will be collected as specified in the Schedule of Trial Procedures (Section 3.0). Please refer to the Laboratory Manual for information on the collection, processing, and shipment of samples to the Central Laboratory.

It is anticipated that the total blood volume drawn will be approximately 250 mL for all cohorts except cohort 3 (fasted and fed), where it will be approximately 415 mL.

Primary specimen collection parameters are provided in Table 9.a.

**Table 9.a** Primary Specimen Collections

[figure not shown]

### 9.3.1 PK Measurements

The PK parameters of TAK-418F will be derived using noncompartmental analysis methods and will be determined from the concentration-time data for all evaluable subjects. Actual sampling times, rather than scheduled sampling times, will be used in all PK computations involving sampling times for plasma PK parameters. Nominal time intervals will be used for computations of urine PK parameters.

The following PK parameters will be calculated as appropriate:

- $t_{max}$ .
- Cmax.
- AUClast.
- AUC\infty.
- CCI

Additional PK parameters may be calculated as appropriate. A detailed PK analysis plan will be prepared before PK parameter computation.

# 9.3.1.1 Plasma for PK Measurements

PK blood samples for plasma TAK-418F concentrations will be collected as specified in the Schedule of Trial Procedures (See Section 3.0).

Plasma TAK-418F concentration will be measured by liquid chromatography with tandem mass spectrometry method.

# 9.3.1.2 Urine for PK Measurements

PK urine samples for urine TAK-418F concentrations will be collected as specified in the Schedule of Trial Procedures (See Section 3.0).

Urine TAK-418F concentration will be measured by liquid chromatography with tandem mass spectrometry method.

### 9.3.2 Biomarker Measurements

### 9.3.3 PGx Measurements

# 9.3.3.1 Blood Sample for DNA and RNA PGx Measurements

Blood samples for DNA and RNA PGx measurement will be taken.

#### CONFIDENTIAL

When sampling of whole blood for PGx analysis occurs, every subject must sign an informed consent/be consented to participate in the trial. PGx is a component of the trial, and participation is mandatory.

PGx is the study of variations of DNA and RNA characteristics as related to drug response. There is increasing evidence that an individual's genetic background may affect the PK (absorption, distribution, metabolism, and excretion), PD (pharmacologic effects) and/or the clinical outcome (efficacy and/or safety).

PGx research in this trial may be conducted to understand how individual genetic variation in subjects affects their trial drug treatment response. This information may also be used, for example, to develop a better understanding of the safety and efficacy of TAK-418 and other trial drugs, to interpret changes in biomarkers, to increase understanding of the disease/condition being studied and other related conditions, to gain a better understanding of the drug pharmacology and for generating information needed for research, development, and regulatory approval of tests to predict response to TAK-418 or to monitor the response to TAK-418.

Whole blood samples for DNA and RNA isolation will be collected from each consented subject in the trial. If necessary and feasible, a second aliquot of blood may be taken at a later time point if isolation of DNA from the first sample was not successful or possible.

Since PGx is an evolving science, many genes and their functions are not yet fully understood. Future data may suggest a role of these genes in drug response, which may lead to additional hypothesis-generating exploratory research and diagnostic development on stored samples.

Detailed instructions for the handling and shipping of samples are provided in the Laboratory Manual.

